2.2.9 Handling of missing values/censoring/discontinuations in efficacy analyses

The detailed censoring for time-to-event is mentioned in previous sections.

Missing date

It is assumed that the day and month of all event dates will be known. If the date's day of the month is missing such that a determination of whether the event occurred within the reporting window cannot be made, the day will be imputed following an attempt to get an approximate date from the family or other records:

- a) if only the month of the event is known, then the 15th day of this month will be imputed for a missing day in case the month and year are after the month and year of double blind treatment start. If the month and year are equal to the double blind treatment start then the event date will be imputed by the treatment start date.
- b) if only the year of the event is known, then the 1st July will be imputed for a missing day and month in case the 1st July is after double-blind treatment start (otherwise treatment start date will be used), or
- c) for events occurring between two visits after randomization, without other information available, the date in the middle of these visits will be used.

An adjudicated death with unknown cause will be classified as a CV death. Similarly, investigator suspected deaths of unknown cause will be classified as CV deaths.

Missing time

For efficacy variables require date and time in calculation, if time is missing or incomplete, the following will be applied:

- a) if hour and minute are both missing, then the 12:00pm (24hr clock) of the day will be imputed in case the hour and minute are after double blind treatment start (otherwise, treatment start hour and minute will be used).

- b) if only minute is missing, 30th minute of the hour will be imputed in case the minute is after double blind treatment start (otherwise, treatment start minute will be used).

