Time points	Hour -16	Hour 0 (Day 1)	Hour 6 (Day 1)	Hour 12 (Day 1)	Hour 24 (Day 1)	Hour 48 (Day 2)	Hour 72 (Day 3)	Hour 96 (Day 4)	Hour 120 (Day 5) b	Discharge e	Day 14	Day 60	Day 120	Day 180 /PSW
Visits	1	101	102	103	104	105	106	107	108		109	110	111	199
Assessment of readmission											X	X	X	X
Administer study medication		X												
Contact IRT/IWRS		X			X									
Adverse and serious adverse events m		X			X	X	X	X	X	X	X			
Follow up completion form														X
Withdrawal of Informed Consent Form p	X													X

PSW = premature patient withdrawal; X= assessment to be recorded on clinical database; S= assessment to be recorded on source documentation

a Study drug treatment will be administered as continuous intravenous infusion for up to 48 hours. Dosage can be adjusted under specific circumstances as described in [Section 5.5.5](#)

b Patients discharged prior to Day 5 will return to the hospital/clinic for Day 5 procedures. Patients unable or unwilling to return to the hospital/clinic will be contacted on or after Day 5 by telephone to obtain information about AEs/SAEs, potential endpoints and survival status.

c Patients discharged prior to Day 14 will return to the hospital/clinic for Day 14 procedures. Patients unable or unwilling to return to the hospital/clinic will be contacted on or after Day 14 by telephone to obtain information about SAEs, potential endpoints and survival status. The Day 60 and Day 180 assessments will be conducted as outpatient visits if the patient is discharged prior. The Day 180 assessments can be performed as early as - 7 days from the timepoint. The Day 120 assessment will be conducted by telephone. Patients unable or unwilling to return to the hospital/clinic for scheduled outpatient visits will be contacted by telephone as close as possible to the expected visit to obtain information about endpoints and survival status. If a patient fails to return for the remaining outpatient visit(s) the investigator should show “due diligence” by contacting the patient, family or family physician up to the time of database lock.

d Procedures performed as part of a site’s standard of care for an individual with AHF can be done during the pre-screening interval and may pre-date the signed ICF.

e If Discharge Visit coincides with a scheduled visit, only the Discharge Visit will be performed.

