2.1.11 Close-out procedure

The number of CV deaths will be predicted on an ongoing basis. [REDACTED]

Subjects who have been randomized to the study will be followed up until their final visit (180 days) or date of death. Attempts should be made to contact any subjects who did not complete the Day 180 visit.

The aim of the close-out procedure will be to allow for all necessary activities (study completion visits, data cleaning, raising and resolution of all queries to the clinical sites, etc.) including the adjudication of all primary and secondary events that occurred during the study and prior to final visit. The “adjudicated endpoint” refers to an endpoint and date of the endpoint that has been confirmed by an independent endpoint committee who has no access to the treatment code.

Only adjudicated events will be counted in the primary analyses. However, sensitivity analyses will be performed on the suspected (investigator reported) primary and secondary endpoints.

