- Time-to-event (days) = date of CV death – randomization date,

For those subjects without events, the censoring date will be the earliest in the following dates:

- **180 days**
- **Date subject withdrew consent to all follow-up (if no subsequent vital status documented)**

Note: in accordance with local laws and regulations, vital status may be publically available

- **Date of non-CV death**
- **Date of subject's last visit or contact or vital status**

The censoring time for the analyses will be calculated as:

- Time-to-event censored (days) = censoring date – randomization date

Whenever the event date or visit date needed for defining the time-to-event or censoring date is missing or incomplete for a given subject, an imputation rule for missing/incomplete date will be applied. More details about the imputation rule are presented in [Section 2.2.9](#).

2.2.3 Time to worsening heart failure (WHF) through Day 5 (considering death in the 5-day period as WHF event)

WHF events occurring within 120 hours of randomization will be included in the analysis. WHF is defined as clinical worsening of HF during the index hospitalization or as adjudicated rehospitalization for HF. A subject who dies by 120 hours without a WHF event will be considered to have had an event at the time of death.

Event date and time will be used at calculating the time to event for better precision, and convert it back to days.

Time-to-event (days) = (first event date/time – randomization date/time),

For those subjects without events the censoring date will be the earliest in the following dates:

- **Hour 120 (5 days)**
- **Date subject withdrew consent to all follow-up**
- **Date of subject's last visit or contact**

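### Two SAP imputation rules, for missing discharge dates and for partial event dates, have no floor at what the record already documents (minor)

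*SAP*

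**What the plan says.** **Length of stay.** SAP 2.2.6.2 measures stay from randomization to index discharge. A patient whose discharge date is missing receives the mean over patients with a known date. In-hospital deaths and patients still in hospital at Day 60 have their own rules. Nothing refers to time already documented in hospital. For the interim analysis, SAP 2.4 treats patients not yet discharged at the cutoff differently: they get the larger of the mean and the stay reached by then.

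**Event dates.** SAP 2.2.9 gives three rules.
- (a) Month known, day unknown: the 15th, unless the month is that of treatment start; "then the event date will be imputed by the treatment start date" in that case.
- (b) Only the year known: 1 July, but only "in case the 1st July is after double-blind treatment start (otherwise treatment start date will be used").
- (c) Event between two visits with no other information: the midpoint of the visits.

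The triggers differ. SAP 2.2.9 imputes when the day is missing "such that a determination of whether the event occurred within the reporting window cannot be made". SAP 2.2.2, for CV death, sends the reader to the same rules more broadly: "Whenever the event date or visit date needed for defining the time-to-event or censoring date is missing or incomplete for a given subject".

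**Worsening heart failure (WHF).** SAP 2.2.3 adds: "A subject who dies by 120 hours without a WHF event will be considered to have had an event at the time of death". An imputed death date can therefore decide event status in this primary endpoint.

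**The concern.** A pre-specified rule should not produce a value that the patient's own record disproves. Rules (a) and (b) can date a death before a visit or call at which the patient was alive. The mean rule can give a patient a shorter stay than the one already recorded. The first touches the two primary endpoints. The second touches length of stay, a key secondary endpoint inside the alpha-controlled testing procedure of SAP 2.2.6.4. Rule (c) would respect an earlier visit, but it needs a visit on each side of the event, and no visit follows a death. The SAP does not say whether it yields to (a) and (b) or overrides them.

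**Working it through.** The plan states no figure on this point, so there is none to reproduce. I applied the rules literally and then sized the effect.

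**1. Literal application**
- *Length of stay.* A patient is documented in hospital on Day 14 and the discharge date is missing. If the overall mean is 10 days (assumed), the rule gives 10 and a floor would give 14.
- *WHF, rule (a).* Treatment starts 3 June, the patient is alive on 5 June, there is no Day 5 contact, and death occurs later in June on an unknown day. The 120-hour status cannot be determined, so even the narrow trigger is met. The imputed date is 3 June, before the live contact, and the death counts as a WHF event. With a floor the date is 5 June, which is still inside 120 hours, so the death still counts.
- *CV death, rule (b), broad trigger.* Treatment starts 1 August, the patient is alive at the Day 120 call (28–29 November), and death occurs in December with only the year recorded. The imputed date is 1 August, about 120 days before the live contact. The death is within 180 days either way; only its time is wrong.

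**2. Length of stay, size**

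Inputs: 6,800 patients and SD 9.6 days (SAP 2.5). Assumptions: 1% of discharge dates missing at random (68 patients), lognormal stays, placebo mean m of 8, 10 or 12 days, serelaxin mean 0.9 days lower with the same SD, and in-hospital status recorded at Day 14.

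Formulas: s = √ln(1 + (9.6/m)²); percentile of the mean = Φ(s/2); P(stay > 14) = 1 − Φ((ln 14 − ln m + s²/2)/s).

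| m (placebo) | percentile of mean | P(>14) placebo | P(>14) serelaxin | 68 × average |
|---|---|---|---|---|
| 8 | 68 | 14.3% | 12.0% | 9.0 |
| 10 | 66 | 20.6% | 17.6% | 13.0 |
| 12 | 64 | 28.4% | 24.7% | 18.1 |

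Using the placebo tail for both arms, the largest value is 68 × 28.4% = 19.3. So about 9–19 patients would be set below a Day 14 stay, in proportion to the missing rate. In one set of lognormal simulations with all 68 missing dates placed in stays over 14 days, the rank-sum Z fell by at most 0.05. That figure depends on the assumed model: the simulated Z was 4.5–5.1, whereas the SAP's 0.9 ± 9.6 days gives 0.9/(9.6 × √(2/3,400)) = 3.87. I do not rely on it.

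**3. WHF, size**

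- All-cause deaths, 3,400 per arm, placebo 11.3%, HR 0.80: 384.2 + 3,400 × (1 − 0.887^0.80) = 384.2 + 311.0 = 695.
- Assume 1% lack the day. The share in the start month and the share of those truly after 120 hours depend on the assumed death pattern. Constant hazard: 695 × 1% × 8.5% × 70% = 0.41. With 10% of deaths early: 695 × 1% × 15.9% × 49% = 0.54. With 20% early: 695 × 1% × 23.5% × 41% = 0.67.
- These are upper bounds, because only patients with no contact after 120 hours are affected. If that is 5–20% (assumed): 0.41 × 5% = 0.02 to 0.67 × 20% = 0.13. At 2% partial dates the top is 0.27.
- For comparison, WHF events at 12.2% and HR 0.80: 414.8 + 336.1 = 751. First-step power at one-sided 0.005, before any alpha is passed on, is Φ(0.2231 × √751/2 − 2.576) = 68.49%. Adding 0.35 events to each arm, more than the estimate supports, gives HR 0.8002 and power 68.45%.

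**4. CV death, size**

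- Events at 9.0% and HR 0.78: 306.0 + 241.1 = 547. At 1% partial dates, rule (a) re-times 547 × 1% × 8.5–23.5% = 0.5–1.3 deaths.
- Moving one death from day t to day 0 removes that patient from the risk sets in between. Approximate shift in logrank Z: (547 × t/180) × (0.5/6,800) ÷ √(547/4).
- t = 15: 45.6 × 0.0000735 ÷ 11.69 = 0.0003. t = 135: 410 × 0.0000735 ÷ 11.69 = 0.0026; simulation gives 0.0024–0.0030, with opposite signs in the two arms.

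**The case against.** The case against is strong on frequency. SAP 2.2.9 presumes that day and month are known and requires an attempt to obtain a date from family or records before imputing. SAP 2.1.11 counts only adjudicated events in the primary analyses, and the term "refers to an endpoint and date of the endpoint that has been confirmed by an independent endpoint committee". The protocol plans a Day 5 visit, and Table 6-1 adds: "Patients unable or unwilling to return to the hospital/clinic will be contacted on or after Day 5 by telephone". The mean rule for length of stay is deliberate: SAP Amendment 2 aligned it with RELAX-AHF, which this trial sets out to replicate. The CV-death example needs the broad trigger of SAP 2.2.2, because under the narrow one the death is known to lie within 180 days. And the date floor does not change event status in the WHF example.

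All of this stands, and it keeps the point minor. It makes such cases rare, but it does not stop the rules, as written, from returning impossible values when they occur.

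A reader might infer more than the documents support:
- *That the interim and final length-of-stay rules contradict each other.* They cover different situations. The interim rule is a precedent for a floor.
- *That a patient documented event-free past 120 hours could be turned into a WHF event.* The trigger in SAP 2.2.9 excludes this, because the window can be determined; the broad wording in SAP 2.2.2 is written for CV death.
- *That the CV-death count, the power or the trial's conclusion is affected.* In the cases above the CV-death count is unchanged, and the shifts are negligible.

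**Conclusion.** The gap is real, and its clearest part is length of stay. Two rules lack a floor at documented facts, the order of the date rules is unstated, and the two triggers do not agree. Severity is minor. No planned figure or expected conclusion changes. The sizes rest on assumptions that the documents cannot confirm: the rates of partial and missing dates, the mean and distribution of stay, the early death pattern, and the share of patients without contact after 120 hours.

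**What to change.** **Length of stay.** For a missing discharge date, use the larger of the mean and the last documented in-hospital time, capped at Day 60. Keep the RELAX-AHF-aligned mean rule as a sensitivity analysis.

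**Event dates.** State the precedence of rules (a)–(c). Reconcile the trigger in SAP 2.2.9 with that in SAP 2.2.2. Never impute a date earlier than the last date documented alive or event-free.

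**WHF.** The floor removes impossible times but does not settle status when status at 120 hours is unknown. State the convention for such deaths and, as a sensitivity analysis, censor them at the last contact.

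**Cost.** A few SAP sentences and small derivation edits before database lock, with no new data. For the date floor, the SAP 2.2.2 censoring rule already uses "Date of subject's last visit or contact or vital status". The one drawback is a small departure from the RELAX-AHF length-of-stay rule, which the sensitivity analysis preserves.

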2.3 Safety evaluation

Safety will be assessed by comparing the study drug to the placebo group with regard to the frequency of AEs, changes in clinical laboratory test results (chemistry and hematology), confirmed blood pressure decreases and vital signs. All safety analyses will be presented for the SAF.

The treatment group will be based on the actual treatment received for each subject.

2.3.1 Adverse events

The incidence of AEs and non-serious AEs recorded through Day 5 and the incidence of SAEs recorded through Day 14 will be presented for the Safety population.

For presentation, AE verbatim text will be coded into a MedDRA (Medical Dictionary for Regulatory Activities) term and classified by MedDRA System Organ Class (SOC) and Preferred Term (PT). The incidence of all reported AEs will be summarized by SOC and PT. A subject reporting the same event more than once will be counted once when reporting the number of subjects with that particular event. Percentages will be based on the number of subjects in SAF.

SAEs will be summarized by time period of onset: from study drug initiation through Day 5 and from Day 6 through Day 14 separately. All AEs through Day 14 will also be provided. Additionally, a summary of AEs by PT and severity, using the worst reported severity grade for each event for the subject, will be provided.

All study-drug-related AEs, AEs leading to discontinuation of study drug, and study-drug-related SAEs, SAEs with an outcome of death, and SAEs leading to study drug discontinuation will be summarized by the number and percentage of subjects reporting particular events. For analysis purposes, if the relationship to study drug is unknown or missing, the AE will be considered to be drug-related.

For the legal requirements of ClinicalTrials.gov and EudraCT, two required tables summarizing treatment emergent adverse events which are not serious adverse events with an incidence greater than 0.5% and summarizing treatment emergent serious adverse events and SAE suspected to be related to study treatment will be provided by system organ class and preferred term on the Safety population.

If for a same subject, several consecutive AEs (irrespective of study treatment causality, seriousness and severity) occurred with the same SOC and PT:

- a single occurrence will be counted if there is ≤ 1 day gap between the end date of the preceding AE and the start date of the consecutive AE
- more than one occurrence will be counted if there is > 1 day gap between the end date of the preceding AE and the start date of the consecutive AE

For occurrence, the presence of at least one SAE / SAE suspected to be related to study treatment / non SAE has to be checked in a block e.g., among AE's in a ≤ 1 day gap block, if at least one SAE is occurring, then one occurrence is calculated for that SAE.

Detailed AE listings will also be provided.

In addition, AEs representing identified and potential safety risk in addition to events of interest will be grouped. The incidence (absolute and relative frequency) of each potential risk will be summarized by treatment group. Odds ratios and associated 95% confidence intervals comparing serelaxin with placebo will be presented using the Mantel-Haenszel test. In addition, subjects experiencing each of these risks will be listed. Such safety risks and events of interest are displayed in below table.

Table 2-7 Safety risk and event of interest search specification

Type of Risk	Specification
Safety risk	
Hypotension	Search terms include the following PTs: Blood pressure ambulatory decreased Blood pressure decreased Blood pressure diastolic decreased Blood pressure immeasurable Blood pressure orthostatic decreased Blood pressure systolic decreased CT hypotension complex Diastolic hypotension Dizziness postural Hypotension Mean arterial pressure decreased Neonatal hypotension Orthostatic hypotension Procedural hypotension Altered state of consciousness Blood pressure abnormal Blood pressure ambulatory abnormal Blood pressure diastolic abnormal Blood pressure fluctuation Blood pressure inadequately controlled Blood pressure orthostatic abnormal Blood pressure systolic abnormal Blood pressure systolic inspiratory decreased Consciousness fluctuating Depressed level of consciousness Dizziness Dizziness exertional Labile blood pressure Loss of consciousness Presyncope

Type of Risk	Specification
	Schellong test
	Syncope
	Tilt table test positive
Hemoglobin/ hematocrit transient decrease	SMQ 'Haemorrhages' (Broad) HLGT 'Anaemias nonhaemolytic and marrow depression'
Fetotoxicity and Teratogenicity	SMQ 'Haematopoietic erythropenia' (Broad) SMQ 'Pregnancy and neonatal topics' (Broad)
Event of interest	
Hypokalemia	Search terms include the following PTs: Alkalosis hypokalaemic Blood potassium abnormal Blood potassium decreased Hypokalaemia Hypokalaemic syndrome Hyperkaliuria Transtubular potassium gradient Urine potassium abnormal Urine potassium decreased Urine potassium increased
Menorrhagia/Metrorrhagia	HLGT 'Menstrual cycle and uterine bleeding disorders'
Potential promotion of cancers	SMQ 'Malignancies' (Broad)
Immunogenicity/Hypersensitivity	SMQ 'Hypersensitivity' (Broad) SMQ 'Angioedema'(Broad) SMQ 'Anaphylactic reaction'(Broad) SOC 'Immune system disorders' HLGT 'Immunology and allergy investigations' HLGT 'Administration site reactions' SMQ 'Severe cutaneous adverse reactions'(Broad)
Cardiac failure	SMQ 'Cardiac failure' (Broad)
QT prolongation	SMQ 'Torsade de pointes/QT prolongation' (Broad) SMQ 'Cardiac arrhythmias' (Broad)
Thromboembolic events	SMQ 'Embolic and thrombotic events'
Renal impairment	SMQ 'Acute renal failure' (Broad)
Respiratory failure	SMQ 'Respiratory failure' (Broad)
Hepatotoxicity	SMQ 'Drug related hepatic disorders – comprehensive search' (Broad)

AEs with an onset between informed consent and study drug initiation will be listed.

For each AE listed, the verbatim term and PT, the corresponding severity, relationship to study drug, seriousness (yes/no), and start and stop date and time of the event will be specified and displayed by treatment group and subject number.

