Serelaxin (and/or matching placebo) will be administered as a continuous intravenous infusion for 48 hours according to a weight-range adjusted dosing regimen at the nominal dose of 30µg/kg/day. Due to the potential risk of hypotension, blood pressure will be monitored regularly during the administration of study drug. If at any time during dosing, the patient's systolic BP is decreased by >40 mmHg from baseline but the absolute systolic BP is  $\geq$ 100 mmHg in two consecutive measurements 15 minutes apart, the study drug infusion rate should be decreased by 50% for the remainder of the infusion period. If the patient's systolic BP falls to <100 mmHg in two consecutive measurements 15 min apart, study drug must be permanently discontinued. Measures may be taken by the investigator to address the decrease in blood pressure during the intervening 15 minutes, if clinically indicated. Should the study drug dose be decreased or the study drug be discontinued prematurely due to blood pressure decrease, then measurements should be taken every half hour through 2 hours following the blood pressure decrease event, and then hourly through 5 hours after event onset. Upon completion of the 5 hour post event onset time point, heart rate and blood pressure measurements should be resumed as outlined in [Section 6.5.2](#). If hypotension persists beyond the 5 hours post event onset, continued hourly blood pressure monitoring should be considered by the investigator, if clinically indicated. Additional blood pressure data collected beyond the 5 hours post event should be captured in the source documents; only heart rate and blood pressure outlined in [Section 6.5.2](#) will be entered into the eCRFs.

All randomized patients will be assessed daily while hospitalized up to Day 5, at Discharge, and then followed up at scheduled visits for a period of 180 days. Patients discharged prior to Day 5 will return to the hospital/clinic for Day 5 procedures. They are required to receive standard-of-care treatment for HF during both the index hospitalization and post discharge per local and institutional practice guidelines. Visits to assess efficacy are scheduled through Day 5, at Discharge, and Days 14, 60, 120 (telephone contact) and 180. For the safety evaluation, all adverse events (AEs) will be collected from signing of the informed consent form through Day 5 for non-serious AEs and through Day 14 for serious AEs.

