### **Study-specific unblinding rules for SUSARs that are commonly observed in the study population**

In clinical trials evaluating treatments for high morbidity and/or high mortality disease states, SAEs that are known consequences of the underlying disease or condition under investigation, or events common in the study population, are anticipated to occur with some frequency during the course of the trial, regardless of drug exposure. While the investigator must still report all non-serious AEs and SAEs through Day 5, and Day 14, respectively, SUSARs considered consistent with the following SAE Preferred Terms will not be unblinded and reported in an expedited timeframe to regulatory agencies, ECs or investigators during the course of the study:

abdominal pain, acute coronary syndrome, acute pulmonary oedema, anaemia, angina pectoris \*, anxiety, arthralgia, asthenia, azotaemia, back pain, blood creatinine \*, blood pressure \*, blood urea nitrogen \*, bronchitis \*, cardiac arrest, cardiac arrhythmias (all Preferred Terms presenting any type of arrhythmia *excluding* electrocardiogram QT interval abnormal, electrocardiogram QT prolonged, long QT syndrome, torsade de pointes), cardiac asthma, cardiac failure \*, cardiac output \*, cardiac pacemaker \*, cardiac tamponade, cardiogenic shock, cardiorenal syndrome, cerebrovascular accident, chest pain, chronic obstructive pulmonary disease, confusional state, constipation, cor pulmonale \*, cough \*, creatinine renal clearance \*, delirium, diarrhea, dizziness, dyspnea \*, ejection fraction \*, fatigue, generalized oedema, glomerular filtration rate \*, gout, headache, hepatic congestion, hyperglycemia, hyperkalemia, hyperlipidemia, hypertension \*, hyperuricaemia, hypoglycemia, hypokalemia, hypernatremia, hypotension \*, implantable defibrillator \*, influenza \*, insomnia, loss of consciousness, muscle spasm, musculoskeletal pain, myocardial infarction\*, nasopharyngitis, nausea, oedema, oedema due to cardiac disease, oedema peripheral, osteoarthritis, pain in extremity, pericardial effusion, pleural effusion, pneumonia \*, presyncope, pulmonary hypertension, pulmonary oedema, renal failure \*, renal impairment, respiratory distress \*, respiratory failure \*, respiratory tract infection \*, stroke\*, syncope, transient ischemic attack, urinary tract infection, valve \*, ventricular failure \*, vomiting, weight increased

\*More than one PT can contain this term.

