2.3.5 Confirmed blood pressure decreases (CBPD)

The number and percentage of subjects who experience a confirmed blood pressure decrease requiring a study drug dose adjustment during study drug administration will be provided. Among subjects who experience a confirmed blood pressure decrease event, the events will be further characterized with respect to impact on study drug administration (dose decreased or

study drug discontinued or both), the timing of event onset relative to study drug initiation, the magnitude of the blood pressure decrease at its onset and the trough blood pressure recorded, the blood pressure measurements after study drug discontinuation, outcome, treatment(s) required, and whether considered symptomatic, i.e. an AE. In addition, these summaries will be provided separately for those confirmed events that resulted in study drug dose reduction, and those that resulted in study drug discontinuation.

Course of blood pressure after the occurrence of first CBPD up to Day 5 will be presented.

To further investigate the impact of CBPD, the following analyses will be performed.

- Baseline characteristics by CBPD subgroup (yes/no).
- Concomitant medications by CBPD subgroup (yes/no).
- CV death through Day 180, WHF through Day 5 and CV death or rehospitalization due to heart failure or renal failure through Day 180 by CBPD impact on study drug administration (dose decreased or study drug discontinued or both).
- AEs associated with the occurrence of the CBPD.

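### The only odds ratio planned for hypotension covers 33 preferred terms, 19 of which do not state low pressure; a low-pressure-only estimate should be pre-specified beside it

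*SAP*

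**What the plan says.** SAP 2.3.1 groups adverse events into safety risks and events of interest. For each group it plans the incidence by arm, a listing of the subjects affected, and an effect estimate: "Odds ratios and associated 95% confidence intervals comparing serelaxin with placebo will be presented using the Mantel-Haenszel test".

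Hypotension is the first safety risk in Table 2-7. Its definition opens with terms that state low pressure: "Search terms include the following PTs: Blood pressure ambulatory decreased Blood pressure decreased Blood pressure diastolic decreased Blood pressure immeasurable". Further down, the same list has blood-pressure terms with no direction, among them "Blood pressure fluctuation Blood pressure inadequately controlled Blood pressure orthostatic abnormal", and symptom terms: "Consciousness fluctuating Depressed level of consciousness Dizziness Dizziness exertional Labile blood pressure Loss of consciousness Presyncope". The row has no narrow and broad version, and no sensitivity analysis is stated for it. Most of the standardised queries in the table are marked Broad; the Hypotension row has no such label.

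The protocol treats low pressure as a recognised risk of the drug. Section 3.1 says: "Due to the potential risk of hypotension, blood pressure will be monitored regularly during the administration of study drug".

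Three other outputs bear on the same risk:
- SAP 2.3.1, AE tables: "The incidence of all reported AEs will be summarized by SOC and PT".
- SAP 2.3.3: descriptive statistics for systolic and diastolic pressure.
- SAP 2.3.5: the number and percentage of subjects with a "confirmed blood pressure decrease requiring a study drug dose adjustment during study drug administration", with further detail on those events.

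**The concern.** A reader of the study report will take the odds ratio on a row called Hypotension as the drug's effect on hypotension. More than half of the terms behind it (19 of 33) do not state low pressure. If those terms occur often and about equally in both arms, they add events to both sides and move the odds ratio toward 1. If they are themselves raised by the drug, they do not. One pooled figure does not show which happened. A group odds ratio near 1.2 could mean a small effect on hypotension or a larger one diluted, and a clearly raised figure could come from dizziness rather than recorded low pressure. What is at stake is the clarity of one summary estimate for a risk that drives the dose-reduction and stopping rules in Protocol 5.5.5.

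**Working it through.** The documents give no rate, odds ratio or power for this group, so there is no planned figure to reproduce. The check has three parts.

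**1. Count of the terms in Table 2-7, by wording**

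| Type | PTs | Content |
|---|---|---|
| States low or unmeasurable pressure | 14 | 7 'decreased' terms (ambulatory, unspecified, diastolic, orthostatic, systolic, systolic inspiratory, mean arterial), 6 hypotension terms, blood pressure immeasurable |
| Blood pressure, no direction | 8 | 5 'abnormal' terms, fluctuation, inadequately controlled, labile |
| Symptom or test | 11 | dizziness (unspecified, exertional, postural), 4 consciousness terms, presyncope, syncope, Schellong test, tilt table test positive |
| Names high pressure | 0 | none |

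14 + 8 + 11 = 33, and 8 + 11 = 19 do not state low pressure. The list is two alphabetical runs joined, of 14 and 19 PTs. These are not quite the same split. The first run contains postural dizziness, and the second contains the systolic inspiratory decrease term. A narrow row therefore has to be defined by naming its terms.

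**2. Size of the attenuation (illustration)**

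Inputs: 6,800 subjects (SAP 2.5) randomised 1:1 (Protocol 5.2), so 3,400 per arm. All rates are assumptions: low-pressure terms 5% on placebo and 7% on serelaxin, and added terms with risk b0 on placebo and b1 on serelaxin, independent of the low-pressure terms.

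Group risk in each arm: P = 1 − (1 − p)(1 − b). Odds ratio (OR) = [P1/(1 − P1)] / [P0/(1 − P0)]. The 95% confidence interval (CI) is exp(ln OR ± 1.96·SE), with SE² = 1/[3,400·P1(1 − P1)] + 1/[3,400·P0(1 − P0)].

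- Low-pressure terms alone: (0.07/0.93)/(0.05/0.95) = 1.43, CI 1.17 to 1.75.
- 2% added in both arms: P0 = 1 − 0.95 × 0.98 = 0.0690 and P1 = 1 − 0.93 × 0.98 = 0.0886. OR 1.31, CI 1.10 to 1.57.
- 5% added in both arms: P0 = 1 − 0.95 × 0.95 = 0.0975 and P1 = 1 − 0.93 × 0.95 = 0.1165. OR 1.22, CI 1.05 to 1.42.
- Added terms with the same odds ratio (5% and 7%): P0 = 0.0975 and P1 = 1 − 0.93 × 0.93 = 0.1351. OR 1.45, so no dilution.

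Other assumed rates show the same pattern. With 4% on placebo and a true OR of 1.50, non-differential terms adding 1%, 3% and 5% per arm give 1.40, 1.29 and 1.23. If 3% of added terms on placebo carry an OR of 1.25, 1.5 or 2.0, the group OR is 1.40, 1.51 or 1.74. Over placebo hypotension rates of 2% to 6%, a true OR of 1.50 becomes 1.34 to 1.43 with 1% added, and 1.14 to 1.28 with 5% added.

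**3. Does another planned output supply the missing estimate?**

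- PT tables (SAP 2.3.1): they cover AEs through Day 5 and SAEs through Day 14, but low pressure is spread over up to 14 separate rows. A subject with two such terms appears in two rows. No count of subjects with any of them is planned, and no odds ratio.
- Vital signs (SAP 2.3.3): descriptive only.
- Confirmed decreases (SAP 2.3.5): limited to falls that lead to a dose change during the infusion, under the thresholds in Protocol Table 5-4. A reported hypotension event after the infusion is outside it, and no odds ratio is stated.

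**The case against.** The strongest reply is that the low-pressure signal will be seen anyway. The PT Hypotension has its own row by arm in the AE tables, over the full collection windows. Pressures are summarised at each time point, and confirmed decreases are described in detail. This stands. It rules out any claim that the overall safety conclusion would be wrong, and it limits the point to one estimate.

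Second, a broad search is a legitimate choice in safety work and fits the rest of Table 2-7. The odds ratio is descriptive and no decision rule hangs on it. This also stands, and it is why the full list should be kept and not cut.

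Third, attenuation is conditional. Dizziness, presyncope and syncope can follow from low pressure, so they may carry a similar or larger effect. Protocol 7.2 lists these symptoms among events that "are anticipated to occur with some frequency during the course of the trial, regardless of drug exposure", but hypotension is on the same list. That passage shows background frequency, not absence of a drug effect.

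A reader might go further and infer that the group mixes effects of opposite sign, because a vasodilator would lower the frequency of too-high-pressure events. The documents do not support this. No listed PT names high pressure. Reading 'inadequately controlled' that way needs the coding dictionary, and the 125 mmHg entry criterion describes screening, not pressure during the infusion. That term is best treated as direction-neutral.

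**Conclusion.** The point holds as a gap in specificity. Table 2-7 plans one odds ratio for a 33-term group, 19 of whose terms do not state low pressure, with no narrow version, and no other output gives a subject-level low-pressure odds ratio through Day 5 (AEs) or Day 14 (SAEs). In the main illustration, non-differential terms at 2% to 5% per arm move an odds ratio of 1.43 to between 1.31 and 1.22. Equally drug-related terms leave it essentially unchanged. Every rate is assumed, and so is independence between the two sets of terms, so the figures show a range and are not a prediction. A reader might infer that the odds ratio will necessarily be pulled toward 1, or that harm would be hidden. Neither follows: the direction depends on the added terms, and the other outputs remain. The severity is minor to moderate.

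**What to change.** In SAP Table 2-7, add a row 'Hypotension (narrow)' that names the 14 PTs stating low or unmeasurable pressure. State that its incidence, odds ratio and 95% CI are the main hypotension estimate. Keep the present 33-PT list as a labelled 'Hypotension (broad)' sensitivity row. No term is deleted, so events coded only as abnormal or labile pressure, dizziness or syncope stay in the risk output, and comparing the two rows shows whether the added terms change the estimate.

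The cost is a table edit and one extra output row, with no new data. The narrow row will miss hypotension coded only under vague terms; the broad row still captures it.
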